We propose a 5-year study to test the effectiveness of a culturally appropriate, theory-based intervention to increase MVPA among Latinas in the LRGV. This study is a continuation of our ENLACE pilot study. We will involve 8 CRCs affiliated with the Colonias Program in the study. The CRCs will be randomized to one of two conditions: (a) ENLACE PA intervention (n=4 CRCs), or (b) attention control (n=4 CRCs). By randomizing at the CRC-level the intervention can be implemented by the promotora to all study participants, thus reducing the risk of contamination that would be present with promotora- or participant-level randomization. This approach also allows us to implement an ecological intervention, where each CRC can implement and promote PA activities and display materials to support the intervention messages. A total of 864 Latinas ages 18-64 years will be recruited from within the service area for these 8 CRCs. The study will be conducted in 3 cohorts of 288 women (36 per CRC in each cohort). Participants will be assessed at baseline, 16 weeks (immediate post intervention), and 40 weeks (delayed post intervention). The primary outcome is minutes per week of MVPA. Secondary outcomes are physical fitness and weight maintenance. Consistent with our approach, we will establish a community advisory group and engage promotoras in conducting participatory community assessments. Finally, we will recruit sub-sample of 4 intervention participants from each CRC cohort to complete two in-depth interviews, immediately following the PA intervention (16 weeks) and after the maintenance intervention period (40 weeks), to evaluate the impact of Latinas’ social and community environment context on their success (or failure) in increasing MVPA and maintaining the behavior change.

Study Design

```

graph TD
    A[8 promotoras] --> B[8 groups of 8-10 women per group (n=68)]
    A --> C[Baseline Assessment N=864]
    C --> D[Randomize]
    D --> E[Physical Activity Intervention (n=432)]
    D --> F[Attention Control (n=432)]
    E --> G[16-week Assessment]
    G --> H[In-Depth Interviews (n=48)]
    H --> I[40-week Assessment]
    I --> J[In-Depth Interviews (n=48)]
    F --> K[16-week Assessment]
    K --> L[40-week Assessment]
    
```

FORM C

IRB #	HSC20110460H
--------------	---------------------

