	C (2) In order to ensure that individuals are appropriately informed about the study when English is their second-language, describe a plan for evaluating the level of English comprehension, and the threshold for providing a translation, or explain why an evaluation would not be necessary. 
Participants will choose their language of preference.

6. Research Plan / Description of the Research Methods:	
6.a. Provide a comprehensive narrative describing the research methods . Provide the order in which tests/procedures will be performed , the setting for these events and a description of the methods used to protect privacy during the study. Provide the plan for data analysis (include as applicable the sample size calculation)	

FORM C

IRB #	HSC20110460H
-------	--------------

Randomization. After baseline data collection, random assignment to experimental condition will use the following procedure: the PI will designate 8 slips of paper as intervention or control (4 intervention, 4 control) and place them into individual sealed envelopes. The sealed envelopes will be shuffled and assigned a number 1 through 8 (written on the outside of the envelope) and given to the Measurement Coordinator in a larger envelope. As each center completes baseline assessments for the first cohort, the Measurement Coordinator will draw an envelope and open it, and will record the CRC name and group assignment into a tracking database. Once randomized, the CRC will remain in the same condition for all 3 cohorts.

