Primary Outcomes (Aim 1 & Aim 2b). MVPA outcomes will be self-reported behavior of a typical week measured with the CHAMPS instrument (minutes/week MVPA) and objective measurement from the accelerometer (minutes/day MVPA). Averages for each MVPA outcome at each time-point will be calculated and compared for the intervention versus the attention-control group and ANOVA tests will be performed to evaluate for significant differences between groups. Assessment will be made to determine direction- e.g. increases or decreases- of change between baseline and post-intervention, and baseline and 6-month follow-up. Using STATA 11 to conduct our modeling we will use a regression that is both multilevel and temporal in nature. Mixed-effects regression can be conducted using the `xreg`, `xtgee` and `xtlogit` command in STATA 11 SE¹⁰², depending on the structure of the outcome variable. In this case, time-points of measurement are nested within subjects in a random intercept model. Random coefficient modeling will be conducted using random effects variables at level 2 (subject level) that will be both fixed (nativity, occupation, education, baseline age, etc.) and time varying (perceptions over time, behavior over time, income). Below we represent the equation for a binomial outcome model

$$\log(\mu_{ij}) = x'_{ij} \beta_1 + x'_{ij} \beta_2 \quad (i = \text{level 1-repeated MVPA measures over time}, j = \text{level 2- Individual level covariates})$$

Whereas β_{ij} represents the expected change in the log of the mean unit change of x_{ij} A one unit change in x_{ij} corresponds to an increase β_{ij} in the log of the average.

Secondary Outcomes (Aim 2a). Similar methodology will be implemented in this analysis as in AIM 1. Our outcome variables

FORM C

IRB #	HSC20110460H
-------	--------------

for aspect of the study will be physical fitness, BMI and anthropometric measures of body fat. Averages for physical fitness, BMI and body fat will be calculated for intervention versus the attention-control group and ANOVA tests will be conducted to evaluate significant cross-sectional differences between the intervention and attention-control groups. Evaluation of temporal changes between each time-point will be made. Mixed effect regression models will be conducted as described in Aim 1.

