Mediation Analyses (Aim 2c). As outlined by MacKinnon^{103, 104}, mediation will be assessed by conducting two regression models. The first model will regress change in the hypothesized mediator (e.g., social support, self-efficacy) on intervention group (intervention vs. control) (α coefficient path). The second model will regress change in the outcome variable (e.g., MVPA) on intervention group and change in the hypothesized mediator (β coefficient path). To assess the magnitude of the effect for each potential mediator, the Sobel-Goodman test will be conducted using *sgmediation* in STATA 11 SE¹⁰⁵. This method provides direct and indirect effect estimates, proportion of effect explained by mediator, and significance testing.

Attrition Analyses. We will compare all baseline demographic, cognitive, and behavioral variables of participants lost to follow-up with baseline data of the cohort, to determine possible selective or differential (by treatment condition) attrition. For instance, analyses will be conducted to determine if participants with greater weight or lower PA disproportionately drop out of the study. Selective attrition (i.e., do dropouts differ from the cohort as a whole?) will be considered a threat to external validity or generalization. Presence of differential attrition (i.e., difference in dropouts between treatment conditions) will be considered a threat to internal validity. To the extent that some subjects are lost to follow-up, analysis for the primary and secondary hypotheses will be carried out under the intent-to-treat principle.

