Qualitative Data Analysis Plan. Audio recordings of interviews will be transcribed verbatim in the source language and returned to the PI in paper and electronic (Microsoft Word) formats. A data collection assistant will review the paper transcripts for quality control purposes to make sure that the paper and electronic transcripts are as accurate and reflective of the interview as possible. All identifying information will be removed from transcripts. The transcript files will be imported into AtlasTi software for qualitative data management and analysis. All data in paper format will be stored in locked cabinets in locked offices. [name] will lead the qualitative analysis of the interview data in the source language, using thematic analysis procedures and the constant comparison method^{97,106}. For presentation and dissemination, selected excerpts of the Spanish-language qualitative data will be translated into English.

Power and Sample Size: Power calculations were conducted to determine the minimum detectable effect size based on a desired power achievement =0.80 using Optimal Design¹⁰¹. Setting the standard effect size to 0.50 and an expected intraclass correlation of .01, we have calculated a minimum number of 83 subjects per site will be needed. Based on a 76% retention rate from the pilot study, we will sample an additional 25 subjects to maintain statistical power throughout study duration for a total of 108 per site and an overall total of 864 subjects.

In-Depth Interviews: With a resulting sample of 96 interviews, we anticipate meeting the requisites of saturation and sufficiency⁹⁶. Saturation refers to the point in the study at which analysis of the interview data results in no new properties or dimensions⁹⁷. The greater the amount of pertinent (on-topic) data obtained from participants, the smaller number of participants required for saturation; thus, well-devised and conducted interviews with skilled probing reduces the need for large sample sizes in order to fully assess the phenomena under study⁹⁸. Sufficiency is the extent to which the participant sample encompasses the range of variability in the participant characteristics, especially those of known relevance to the topic⁹⁹. Due to the relative homogeneity of our participants, a sample of 96 interviews is expected to be sufficient.

6.b. List of the study intervention(s) being tested or evaluated under this protocol

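### The stated MVPA analysis has no CRC level although CRCs are randomised: the time-point ANOVA runs at about 14.5% type I error, the longitudinal test at about 5% to 22%

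*Protocol*

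**What the plan says.** **Design.** Allocation is by center (Protocol, item 3, D.2.1 Overview of Study Plan and Design): "By randomizing at the CRC-level the intervention can be implemented by the promotora to all study participants". Item 6.a, Randomization, describes a single draw of four intervention and four control assignments and adds: "Once randomized, the CRC will remain in the same condition for all 3 cohorts". There are therefore eight randomised units, however many cohorts or women follow.

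**Sample size.** Item 6.a, Power and Sample Size, recognises that women from one CRC resemble each other: "Setting the standard effect size to 0.50 and an expected intraclass correlation of .01". It arrives at 83 women per site, raised to 108 for 76% retention, 864 in all.

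**Analysis.** Item 6.a, Primary Outcomes (Aim 1 & Aim 2b), takes averages of each MVPA outcome at each time-point and says that "ANOVA tests will be performed to evaluate for significant differences between groups". It then describes a regression, called multilevel, in which "In this case, time-points of measurement are nested within subjects in a random intercept model". The text places the covariates at level 2, the subject. The key to the equation repeats this: level 1 is the repeated MVPA measures and level 2 the individual. No CRC random effect, cluster-robust variance, CRC-level summary or cluster-based degrees of freedom is mentioned.

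**Other analyses.** Secondary Outcomes (Aim 2a) adopts the same approach. Mediation Analyses (Aim 2c) lists its regressors, starting with "The first model will regress change in the hypothesized mediator" on intervention group, and names no CRC term.

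**The concern.** When centers are randomised, the arm difference contains the difference between two sets of four centers. Women at one CRC share a promotora, a group, a building and a neighbourhood. A subject random intercept absorbs correlation between repeated measures on one woman. It does nothing for correlation between women at the same CRC. An analysis that stops at the subject counts several hundred women as independent evidence on treatment when there are eight randomised units and 8 − 2 = 6 degrees of freedom between them.

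The trial could therefore report an effect on MVPA that is only variation between centers. The sample size and the analysis also describe different tests, since one allows for the ICC and the other does not.

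**Working it through.** **Inputs.** From the Protocol: 8 CRCs, 4 v 4; ICC .01; standardised effect 0.50; power 0.80; 83 per site needed, 108 enrolled; retention 76%. Assumed: two-sided 5% tests, as no alpha is stated for the tests. For the longitudinal model only, also assumed: total CRC variance .01 of a total of 1, and within-woman correlation 0.5.

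**1. The plan's own figure.** For m women in each of J = 8 CRCs, the variance of the arm difference in SD units is 4 × [ICC + (1 − ICC)/m] / J, tested by t on 6 df. At effect 0.50 and ICC .01, 80% power needs m = 30. The stated 83 is not reproduced; it gives about 97.6% power. The rest of the chain is close: 83 + 25 = 108, 108 × 8 = 864, and 108 × 0.76 = 82 retained against 83 needed. The 83 is a separate matter, but it means there is power to spare for a correct test.

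**2. Time-point ANOVA.** With two arms this is a two-sample test on individuals. The design effect is DE = 1 + (m − 1) × ICC, and the true error is 2 × [1 − Φ(1.96/√DE)].

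- m = 82: DE = 1 + 81 × .01 = 1.81; √DE = 1.345; 1.96/1.345 = 1.457; error 14.5%. Simulation gives 14.4% to 15.2%.
- m = 108: DE = 1 + 107 × .01 = 2.07; 1.96/1.439 = 1.362; error 17.3%.
- m = 82 at other, assumed ICCs: 5.9% (.001), 9.8% (.005), 22.6% (.02), 38.3% (.05).

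At m = 82 and ICC .01, a correct 95% interval is 1.345 × 2.447/1.96 = 1.68 times as wide as the naive one.

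**3. Arm-by-time test in the subject-random-intercept model.** With two time-points this amounts to comparing individual changes. A CRC effect that is stable over time cancels from the change. If v is the CRC variance that varies by time, the CRC part of the change has variance 2v, and the individual part 2 × .99 × (1 − 0.5) = .99. The ICC of change is 2v/(2v + .99), which goes into the formula of step 2 with m = 82.

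| v (of .01) | ICC of change | DE | Error, formula | Error, simulation (10,000 runs) | t-test on CRC mean changes, 6 df (simulation) |
|---|---|---|---|---|---|
| 0 | 0 | 1.00 | 5.0% | 5.5% | 5.0% |
| .002 | .0040 | 1.33 | 8.9% | 9.2% | 5.1% |
| .005 | .0100 | 1.81 | 14.5% | 14.3% | 5.1% |
| .01 | .0198 | 2.60 | 22.5% | 22.5% | 5.3% |

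The CRC-level test holds close to 5% throughout.

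**4. Power of the corrected test.** Step 1's formula with m = 82 and effect 0.50 gives a noncentrality of 4.76 and power of about 97% at ICC .01. At an assumed ICC of .02 power is about 91%, and at .05 about 66%.

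**The case against.** Four points can be made for the plan.

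- **The regression is called multilevel, and a SAP may complete it.** The first part fails because the levels are spelled out twice and end at the subject. The second would hold if the Protocol were silent. Here it states a model, and that model conflicts with its own randomisation and ICC.
- **The longitudinal model is less exposed than the ANOVA.** This stands. A reader might infer that the 14.5% applies to the quoted random-intercept model, or that every p-value and interval in the plan is too optimistic by that amount. The Protocol does not support this. The figure is for a comparison of arms at one time-point. For arm-by-time the error could be near nominal if centers differ only by a constant amount, and could exceed 14.5% if their differences shift between visits. No figure in the Protocol says which.
- **The mediation section does not say how standard errors are obtained.** This also stands. One may say that no CRC term is named, but not that the regressions are stated to treat women as independent.
- **The ANOVA may be meant as description.** It is written as a test for significance, in a paragraph that follows the descriptive work. Demoting it alone would still leave a regression without a CRC level.

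**Conclusion.** The stated primary analysis does not match the design and should be changed before it is used. The ANOVA result rests on the Protocol's own ICC and retention plus a two-sided 5% test: about 14.5% true type I error with 82 women per CRC and about 17% with 108. The longitudinal result is a range, about 5% to 22%, under an assumed total CRC variance of .01 and within-woman correlation of 0.5. Where the trial falls in it depends on CRC-by-time variance that the Protocol does not give.

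A reader might also infer that a correct analysis would leave the trial underpowered. At the Protocol's effect and ICC it does not; that would become a concern only if the ICC were nearer .05, which is an assumption and not the Protocol's value.

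**What to change.** 1. Make one of these the primary test:
   - a t-test on 6 df comparing the eight CRC-level means of baseline-adjusted follow-up MVPA, or of change in MVPA (the simpler choice); or
   - a mixed model with random effects for participant, CRC and CRC-by-time, with the arm-by-time contrast tested on about 6 df.

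   The CRC-by-time term is essential. A CRC random intercept by itself largely cancels from the arm-by-time contrast and leaves its standard error essentially unchanged.
2. As a check, add a permutation test over the 70 ways of choosing 4 of 8 CRCs. Its smallest two-sided p-value is 2/70 = 0.029, so it can reach 5%.
3. Keep the time-point averages as description and drop the individual-level ANOVA as an inferential test.
4. Use the same approach for the secondary outcomes, and say how CRC is accounted for in the mediation regressions.

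**Cost.** Analysis wording and wider intervals. No extra participants or data are needed at the Protocol's effect size and ICC.

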D.4.2.4. Environmental Change. Social ecological models^{33, 34, 78} emphasize that the environment is an important influence on health behavior. We will work with *promotoras* at the four ENLACE PA intervention CRCs to create a site atmosphere that promotes PA. Examples might include educational posters, promotional activities to increase awareness and appeal of existing resources, notices of related community events, and a display board highlighting the ENLACE Program and participants who have been successful in the program. *Promotoras* will also increase the number of PA program offerings at the CRC by identifying and training volunteer walk leaders and using an exercise DVD library to offer regularly scheduled group exercise classes.

D.4.2.5. Attention Control Intervention. Attention control participants will receive a research-tested first aid and home safety program developed for Hispanic migrant adolescents and their families⁷⁹. We selected the home safety/first aid as the attention control condition because changes in these behaviors should have no impact on PA, the curriculum is available in Spanish, and has been shown to improve first aid knowledge and emergency response skills. In addition, the *Colonias* Program staff indicated it was relevant topic for families in the *colonias*. The program includes 8 sessions that last 1.5-2 hours. These sessions will be offered twice per month to extend them over a 16 week period. The session content ranges from identifying household safety hazards to disaster preparedness. During the 24 week maintenance phase, *promotoras* will contact participants by phone each month and conduct monthly home visits to distribute health education materials on first aid and home safety from CDC, state health department and other reliable health organizations (e.g., Red Cross). Attention control participants will not receive telephone counseling calls.

Measurement and Evaluation

Standardized data collection protocols will be carried out for all participants at baseline, 16-, and 40-weeks.

Primary Outcome Measures:

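### The MVPA regression is described inconsistently, and the one model stated that can be run, a subject random intercept, assumes equal correlation among visits at 0, 16 and 40 weeks

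*Protocol*

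**What the plan says.** All of the following stands in one paragraph of Protocol section 6.a, Primary Outcomes (Aim 1 & Aim 2b).

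- **Commands.** Mixed-effects regression "can be conducted using the `xreg`, `xtgee` and `xtlogit` command", the choice depending on the structure of the outcome. The first is read here as `xtreg`.
- **Random intercept.** The text says "time-points of measurement are nested within subjects in a random intercept model".
- **Random coefficients.** The next sentence says "Random coefficient modeling will be conducted using random effects variables at level 2 (subject level) that will be both fixed (nativity, occupation". The list goes on to education and baseline age, then to a time-varying group: perceptions, behavior and income.
- **Equation.** A log-mean equation follows, introduced as being for a binomial outcome. It has two fixed-effect terms and no random term. Its first index is labelled as repeated MVPA measures.

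Elsewhere, section D.2.1 gives the primary outcome as minutes per week of MVPA. Under Measurement and Evaluation, standardized data collection "will be carried out for all participants at baseline, 16-, and 40-weeks", while demographic data, including education, occupation, nativity and family income, are collected at baseline only. Randomization is by CRC: "ENLACE PA intervention (n=4 CRCs), or (b) attention control (n=4 CRCs". The secondary-outcome paragraph (Aim 2a) takes over the same mixed models.

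**The concern.** Two things are at issue.

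**Fit between the statements.** Nativity, education and baseline age have one value per woman. A woman-specific slope on such a trait cannot be told apart from her random intercept; it only lets the between-woman variance differ with the trait. It says nothing about how her visits correlate. Nor do the listed commands fit random coefficients: `xtgee` fits no random effects, and `xtreg` and `xtlogit` fit a random intercept only. A binomial log-mean equation does not describe a continuous outcome in minutes.

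**Consequence of what can be run.** That leaves the random intercept, which gives every pair of visits the same correlation. The gaps are 16 weeks (0 to 16), 24 weeks (16 to 40) and 40 weeks (0 to 40), so the baseline to week-40 correlation may well be the lowest. The within-woman covariance sets the standard error of each change-from-baseline contrast, and the plan does evaluate change from baseline to both follow-ups. An error there affects the confidence intervals and tests for Aim 1 (week 16) and, more, Aim 2b (week 40).

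**Working it through.** **Inputs.** The visit times and the outcome scale come from the protocol. It gives no visit correlations, so there is no figure of its own to reproduce, and the correlations below are assumptions. Also assumed: equal variance at the three visits (set to 1), complete data, a two-sided 5% test and, for this part, no CRC variance.

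**Formulas.** Let ρ₀ₜ be the true correlation between baseline and visit t, and ρ̄ the mean of the three pairwise correlations.

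- True variance of a woman's change: 2(1 − ρ₀ₜ).
- Variance implied by the random intercept, whose residual variance is pooled over the three visits: 2(1 − ρ̄).
- Ratio of true to model standard error: R = √[(1 − ρ₀ₜ)/(1 − ρ̄)].
- False-positive rate: 2·P(Z > 1.96/R).

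**Results.** Correlations are in the order 0-16, 16-40, 0-40.

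| Assumed correlations | 1 − ρ̄ | Week 16: R, error | Week 40: R, error |
|---|---|---|---|
| 0.6, 0.6, 0.4 | 0.4667 | √(0.4/0.4667) = 0.926, 3.4% | √(0.6/0.4667) = 1.134, 8.4% |
| 0.5, 0.6, 0.5 | 0.4667 | √(0.5/0.4667) = 1.035, 5.8% | 1.035, 5.8% |
| all 0.5 | 0.5 | 1, 5% | 1, 5% |

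In the first row the model's standard error is too small by a factor of 1.134 at week 40 and about 8% too large at week 16 (1/0.926 = 1.08).

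**Simulation check.** With three visits, 332 women per arm (4 × 83, the protocol's minimum per site), no CRC variance and 4000 null runs, the first pattern gave 8.8% at week 40 and 3.3% at week 16. Equal correlation of 0.5 gave 4.8% and 4.9%.

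**Two visits cannot show this.** A simulation with baseline and one follow-up gave 5.3% to 6.0% for the random intercept without CRC variance. With two visits there is only one correlation, so that result does not bear on unequal correlation among three.

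**CRC level, for scale.** The power section says "Setting the standard effect size to 0.50 and an expected intraclass correlation of .01", yet the highest level in the regression is the woman. In the two-visit simulation with 83 women per CRC and a CRC variance of 0.01 drawn independently at each visit (an assumption), the random-intercept test of change rejected in 18% to 33% of null runs for within-woman correlations of 0.3 to 0.7. A test on CRC means with 8 − 2 = 6 degrees of freedom rejected in 5.0% to 5.3%. A CRC effect constant over time would cancel out of change and do less harm.

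**The case against.** **A random intercept is a legitimate model.** It is valid when the visit correlations are equal, and only mildly off under 0.5/0.6/0.5. This stands. A reader might infer that the standard errors are wrong whichever description is followed; the documents do not support that, because they give no correlations.

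**`xtgee` is on the list.** It can take an unstructured working correlation with robust standard errors, so a named command could handle unequal correlation. This stands too, but the paragraph specifies neither, and the model it names is the random intercept.

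**The descriptions are not strictly incompatible.** A random intercept is a special case of a random-coefficient model, and the same sentence lists time-varying variables, whose slopes can be separated from the intercept. Inconsistent is therefore the fair word. Even so, the listed commands fit no random slopes, and income, listed as time varying, is among the items collected only at baseline.

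**The equation need not show the covariance.** A reader might infer that the printed equation assumes independent visits, which would make standard errors of change 1.29 to 1.58 times too wide for correlations of 0.4 to 0.6. That goes too far: a mean equation can omit the covariance, and the text names a random intercept shortly before it. What remains is the binomial form for an outcome in minutes.

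**Limited scope.** The plan also compares arms by ANOVA at each time point. Within-woman covariance does not enter a single-visit comparison, so those tests are not affected by this point.

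**The SAP may settle the covariance.** Leaving it open would be no finding. Here the protocol does not leave it open: it fixes an intercept structure, random coefficients, commands and an equation, and these do not fit together.

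**The missing CRC level matters more.** This probably stands. It does not remove the present point, since a CRC term alone leaves the within-woman covariance unchanged, but a remedy without a CRC term would leave the larger error.

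**Conclusion.** The concern holds in limited form. The MVPA regression is described inconsistently, part of it cannot be fitted as written, and the equation does not suit the outcome. The random intercept may misstate standard errors of change from baseline if the three correlations differ, most at week 40 if the baseline to week-40 correlation is the lowest.

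The size depends on assumed correlations: a week-40 false-positive rate of about 8.4% under 0.6/0.6/0.4, 5.8% under 0.5/0.6/0.5 and 5% under equal correlation. At week 16, the primary aim, the test may be slightly conservative (3.4%) or slightly liberal (5.8%). These rates take CRC variance as zero, so they isolate this one issue and do not forecast the trial's overall error rate. The change is worth making because the remedy is cheap.

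**What to change.** In section 6.a, Primary Outcomes:

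1. Delete the random-coefficient sentence as it applies to baseline traits, and the binomial equation for MVPA.
2. State one linear mixed model for MVPA minutes with an unstructured 3×3 covariance for the three visits within woman (in Stata, for example, `xtmixed`), in place of the present command list for this outcome.
3. Enter nativity, occupation, education and baseline age as ordinary fixed effects.
4. Include a CRC-level term in the same model, because CRCs are the randomized unit. It should allow CRC effects to differ by visit, since a constant CRC effect cancels out of change. Refer arm contrasts to about 6 degrees of freedom (8 − 2).
5. Carry the same wording to the continuous secondary outcomes that take over this method.

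**Cost.** This changes wording only and needs no new data. The within-woman part has six covariance parameters (three variances, three covariances) instead of two, which is negligible with up to 864 women. The CRC term will widen the intervals where centers differ, as the randomization requires.
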